3.2.12 Inability or unwillingness to provide consent

3.2.13 Current or recent treatment (within the last 14 days from screening) with niacin/nicotinamide $> 100 \text{ mg/day}$

3.2.14 Current or recent use of MVI containing niacin/nicotinamide $> 100 \text{ mg/day}$

3.2.15 Current use of Tums (or calcium carbonate taken for indigestion) at a dose of $> 1000 \text{ mg daily}$

3.2.16 Current participation in another clinical trial or other interventional research

3.3 WOMEN OF CHILD-BEARING POTENTIAL

3.3.1 Should a woman become pregnant or suspect she is pregnant while participating in this study, she should inform her treating physician immediately. A female of child-bearing potential is any woman (regardless of sexual orientation, having undergone a tubal ligation, or remaining celibate by choice) who meets the following criteria:

- Has not undergone a hysterectomy or bilateral oophorectomy; or
- Has not been naturally postmenopausal for at least 12 consecutive months (i.e., has had menses at any time in the preceding 12 consecutive months).

- Pregnancy or planning to become pregnant or currently breast-feeding. Women of childbearing potential (pre-menopausal and not surgically sterilized) will have pregnancy test before enrollment

4.0 TREATMENT PLAN

4.1 Treatment Dosage and Administration

4.1.1 Overview:

Eligible participants will be randomized to one of the following 4 groups:

- Lanthanum carbonate + nicotinamide
- Lanthanum carbonate + nicotinamide placebo
- Lanthanum carbonate placebo + nicotinamide
- Lanthanum carbonate placebo + nicotinamide placebo

4.1.2 Regimen description is presented in the table below.

Agent	Dose	Route	Schedule	Cycle Length
Nicotinamide	750 mg twice daily	By mouth	Daily for 2 weeks	2 weeks (14 days)
Lanthanum carbonate	1000 mg three times daily with meals	By mouth	Daily for 2 weeks	

Lanthanum carbonate is a chewable tablet. Lanthanum carbonate binds ingested phosphorus in the gut and therefore only works when taken with meals. Participants who do not eat regular meals will be instructed to take full doses with larger meals and half with snacks. Nicotinamide can be taken together with lanthanum carbonate at breakfast and at dinner.

4.2 Toxicities and Dosing Delays/Dose Modifications

Lanthanum carbonate may lower blood phosphate levels and can be associated with gastrointestinal side effects including nausea, vomiting, constipation and diarrhea.

Nicotinamide may lower blood phosphate levels and may be associated with other laboratory abnormalities including thrombocytopenia, abnormalities in liver function tests and CK. Gastrointestinal side effects, such as diarrhea and heartburn may also occur.

The following laboratory results are **expected study adverse events**:

- **Hypophosphatemia:** Plasma phosphate level <1.5 mg/dl
- **Thrombocytopenia:** Platelet count <100,000
- **Liver function test abnormalities:** AST, ALT, total bilirubin, alkaline phosphatase > 4 times the upper limit of the core lab (fill in precise numbers when the lab is named)
- **Elevated Creatine Kinase:** Creatine Kinase > 4 times upper limit of normal

The following symptoms are **expected study adverse events**:

- **Bruising**
- **Bleeding**
- **Severe diarrhea**
- **Severe nausea**
- **Flushing**
- **Hives**

Each patient will be assessed for the development of toxicity at each study visit (see section 5.4).

4.3 Concomitant Medications/Treatments

Calcium carbonate tablets taken for indigestion, such as Tums, are allowed if taken once per day or less, at least 2 hours away from meals and at a maximum dose of 1000 mg daily. However, participants who report using Tums often will be encouraged to try over-the counter Pepcid (famotidine), Tagamet (cimetidine), or Zantac (ranitidine).

Non-study source of vitamin B3 (niacin or nicotinamide) as a stand- alone medication or in a multivitamin that contains less than 100 mg/day of nicotinamide is allowed. Larger doses are to be avoided.

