2.0 STUDY OBJECTIVES

2.1 Primary Objectives

2.1.1 To determine the short-term effects of lanthanum carbonate and nicotinamide, alone and in combination, on phosphate handling, as measured by plasma phosphate, 24-hour urinary phosphate and fractional excretion of phosphate in healthy volunteers

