5.2 Screening Procedures

Assessments performed exclusively to determine eligibility for this study will be done only after obtaining informed consent.

The screening procedures include:

5.2.1 *Informed Consent*

Consent form will be reviewed in full with each subject.

5.2.2 *Medical history and Physical Exam*

Complete medical and surgical history will be obtained from each subject, and a physical exam will be performed on each subject.

5.2.3 *Demographics*

Subject will be queried on age, gender, race, and ethnicity

5.2.4 *Review subject eligibility criteria*

Study personnel will review inclusion/exclusion criteria with every subject to determine eligibility.

5.2.5 *Review previous and concomitant medications, including multivitamins*

5.2.6 *Vital signs, height and weight*

Blood pressure, height, and weight will be obtained on each subject.

5.2.7 *Hematology*

CBC

5.2.8 *Plasma chemistries and Serum 25-Hydroxyvitamin D*

To include: albumin, alkaline phosphatase, ALT/SGPT, AST/SGOT, BUN, creatinine, electrolytes (sodium, potassium, chloride, bicarbonate), glucose, and total bilirubin; phosphorus; calcium; CK; and 25-hydroxyvitamin D

5.2.9 *Random urine*

To include: creatinine and albumin

5.2.10 *Supplies for 24-hr urine collection*

5.2.11 *Rapid Urine Pregnancy test (for females of child bearing potential)*

See section 3.1.6.1 for definition.

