5.4.2 Follow-up Visits 1 – 4 (F1-F4)

- Return 24-hour urine collection to measure phosphorus, creatinine, calcium, and urea in the urine
- Plasma chemistries(NA, K, Cl, HCO3, BUN, Cr, glucose, calcium)
- Blood draw for correlative studies (PTH, FGF23)
- Random urine sample to measure phosphorus, creatinine, and calcium in the urine
- Distribute supplies for next 24-hr urine collection
- Bring in pill bottles for pill counts
- Safety assessments (phosphate, CK, CBC, LFTs, GI Questionnaire)

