5.5 Time and Events Table

Periods	SCREENING	BASELINE		Follow UP				
		F1	F2	F3	F4	F5		
Visits	S1	B1	B2/F0					
Days	-15	-5	-2	0	3	6	9	12
Pregnancy testing	X							
RANDOMIZATION				X				
Distribute drug/placebo (X=21 day supply)				X				
Demographics, medical history, physical exam	X							
Vital signs (blood pressure, height, weight)	X							
Co-Primary end-points								
FePI/ Spot Urine phosphate, calcium, and creatinine		X	X	X	X	X	X	X
24-hr urine phosphate, creatinine, calcium, and urea		X	X	X	X	X	X	X
8 hr urine phosphate, creatinine, calcium, and urea		X						X
Spot Urine (creatinine, albumin)	X							
Other mineral metabolites								
PTH		X	X	X	X	X	X	X
FGF23		X	X	X	X	X	X	X
P1NP (bone metabolism marker)		X						X
CTX (bone metabolism marker)		X						X
25 hydroxyvitamin D	X							
Plasma Phosphate	X	X	X	X	X	X	X	X
Plasma Calcium	X	X	X	X	X	X	X	X
Renal parameters								
Chem 7 (Na, K, Cl, HCO3, BUN, Cr, glucose)	X		X	X	X	X	X	X
Plasma Creatinine		X						
Stored blood samples (optional)		X						X
Stored urine samples (optional)		X						X
CBC, LFTs, CK	X			X	X	X	X	X
Adverse events assessment (labs and GI questionnaire)				X	X	X	X	X
Pill Count				X	X	X	X	X

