10.3 Data Analyses Plans

- We will study changes over time in absolute levels of the primary and secondary end-points.
- We will use mixed-model, repeated-measures analyses to assess the changes.
- Model terms will include:
 - fixed-effects treatment terms (treatment group);
 - the interaction between each treatment and time (nicotinamide x time and lanthanum carbonate x time);
 - the interaction between treatments (nicotinamide x lanthanum carbonate);
 - the interaction between treatments and time (nicotinamide x lanthanum carbonate x time);
 - random-effects terms, connoting individual participants.
- If the interaction term between treatments and time (nicotinamide x lanthanum carbonate x time) is significant, we will compare the response in the dual intervention group to the placebo group.
- If the interaction term between treatments and time (nicotinamide x lanthanum carbonate x time) is not significant, we will examine the main effects of each intervention.
- We will use natural log transformation for end points with skewed distribution.
- If there are significant differences ($p<0.05$) in age, gender and baseline eGFR across randomized treatment groups, we will adjust for these covariates.
- Standard descriptive analyses will be used for safety evaluations.

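### Cimetidine, one of the antacid substitutes suggested in section 4.3, can shift the creatinine-based primary end point FePI without any change in phosphate handling: very small expected effect, simple fix, lowest priority

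*Combined protocol and SAP*

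**What the plan says.** Section 4.3 (Concomitant Medications/Treatments) allows limited calcium carbonate for indigestion and then states that "participants who report using Tums often will be encouraged to try over-the counter Pepcid (famotidine), Tagamet (cimetidine), or Zantac (ranitidine". It expresses no preference among the three drugs, sets no timing, and gives no caution about creatinine.

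Section 2.1 makes FePI a primary measure, alongside plasma phosphate: "24-hour urinary phosphate and fractional excretion of phosphate in healthy volunteers". The formula is not written out. The Time and Events Table (section 5.5) has a row for "FePI/ Spot Urine phosphate, calcium, and creatinine" at all seven visits from B1 to F5. Plasma creatinine is drawn at the same seven visits, on its own row at B1 and after that within "Chem 7 (Na, K, Cl, HCO3, BUN, Cr, glucose".

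The only listed medication review is in the screening procedures (section 5.2): "Review previous and concomitant medications, including multivitamins". The table puts screening at day -15 and B1 at day -5. Exclusion 3.2.15 removes heavier antacid users: "Current use of Tums (or calcium carbonate taken for indigestion" above 1000 mg daily. Follow-up visits include "Safety assessments (phosphate, CK, CBC, LFTs, GI Questionnaire", but the questionnaire's items are not shown. Section 10.3 has no term for concomitant medication. It does say: "We will use natural log transformation for end points with skewed distribution".

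**The concern.** A primary end point built on creatinine should not be exposed to a drug that changes creatinine by itself, least of all one that the protocol suggests. If cimetidine raises plasma creatinine while filtration and phosphate excretion stay the same, computed FePI rises although the kidney handles phosphate exactly as before. In a trial of phosphate handling, such a rise could be misread as a renal effect of study drug.

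Timing decides whether this matters. A participant who takes cimetidine steadily from before B1 carries the same factor at every visit. One who starts, stops or uses it intermittently after B1 has a change over time that comes from measurement. Section 4.3 is not limited to screening, and section 4.2 lists heartburn as a possible nicotinamide side effect, so a start on treatment is conceivable. The documents give no frequency for it, and no direction of imbalance between arms is claimed here.

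**Working it through.** **The plan's own figures.** Section 10.2 gives 80% power with 20 per group for a difference of 273 with SD 300 (24-hour urine phosphate), and for 0.50 with SD 0.55 mg/dl (plasma phosphate). A two-sided t test reproduces both (power 0.801 and 0.800). The plan gives no SD or power for FePI, and neither stated figure depends on this point.

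**Inputs from the documents.** Four cells of 20, hence margins of 40 (sections 10.1 and 10.2). Seven FePI visits, on the table's day values after screening: -5, -2, 0, 3, 6, 9, 12 (section 5.5). Mixed model with treatment-by-time terms and participant random effects (section 10.3).

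**Assumptions, none from the documents.** Plasma creatinine rise 10–30%; baseline FePI 12%; within-subject CV of FePI 15–35%; SD of change in FePI 3–5 percentage points; the numbers and rates of users.

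**One participant.** The standard formula is FePI = (urine phosphate × plasma creatinine) / (plasma phosphate × urine creatinine). With the other three terms fixed, FePI scales with plasma creatinine: 12% × 1.1, 1.2 and 1.3 = 13.2%, 14.4% and 15.6%.

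**Shift in a margin mean.** With k extra users in one margin of 40, the relative shift on the log scale is (1 + rise)^(k/40) - 1.
- k = 1: 0.24–0.66%
- k = 2: 0.48–1.32%

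**Type I error, treatment × linear time.** Log FePI, random intercept, users on cimetidine at the last five visits. The worst case shown is k = 2, rise 30%, CV 15%:
- Margin shift: ln(1.3) × 2/40 = 0.01312.
- Mean day 3.286; sum of squared deviations 223.43; sum of deviations over the last five visits 30 - 5 × 3.286 = 13.57.
- Slope bias: 0.01312 × 13.57 / 223.43 = 0.000797 per day.
- Within-subject SD: √ln(1 + 0.15²) = 0.149. Standard error of the slope difference: 0.149 × √(2 / (40 × 223.43)) = 0.00223.
- Non-centrality: 0.357. Non-central t with 476 df gives 6.47%.

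**All scenarios** (ranges over the assumed rises and CVs; F5-only row at a 30% rise):

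| Scenario | Linear time | Categorical time (F, 6 and 456 df) |
|---|---|---|
| 1 extra user, last five visits | 5.01–5.36% | 5.01–5.21% |
| 2 extra users, last five visits | 5.04–6.47% | 5.02–5.86% |
| 2 extra users, F5 only | 5.12–5.60% | 5.10–5.51% |
| Stable use from before B1 | 5.00% | 5.00% |

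With both users in the dual-treatment cell, the nicotinamide × lanthanum × linear time term also gives 5.04–6.47%. A simple t test on change (40 v 40, SD 3–5 points) gives 5.01–5.20% for one extra user and 5.03–5.81% for two.

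**Chance imbalance.** If 2.5%, 5% or 10% of participants started after baseline regardless of arm, the probability that two groups of 40 differ by five or more users is 0.26%, 2.2% or 9.2% (difference of two binomials).

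**The case against.** The strongest reply is that nothing in the plan is wrong and the result is not at risk.

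- **Few people, mostly harmless timing.** Users above 1000 mg/day are excluded and cimetidine is one of three options. Most switches would probably follow the screening review, ten days before B1, and stable use then largely cancels. This stands, and it is why the point has the lowest priority.
- **The type I error figures presuppose an imbalance.** They place one or two extra users in one margin. Use unrelated to arm causes no inflation: a simulation with 2.5–10% random starters, a 30% rise and CV 15–25% rejected 4.5–5.4% of the time over 4,000 runs per setting. This also stands. The figures show how much an imbalance would do, not that one is expected.
- **Inputs from outside the documents.** The creatinine effect, its size at over-the-counter doses, and the FePI variability are assumed, and the formula is inferred from the samples collected. This is correct, so ranges are shown. The direction follows from the ratio.
- **Visit timing is uncertain.** Section 5.4.1 puts randomization at B2/F0, whereas the table as extracted marks it in a later column. If only the last four visits were exposed, two extra users would give 5.06–7.27% (linear time). The conclusion does not change.
- **Not quite free.** Section 11.7 requires IRB approval of a written amendment, and participants get one more restriction. This is true, but both are minor.

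The case report forms and the questionnaire are not shown, so it cannot be said that acid-reducer use goes unrecorded.

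**Conclusion.** The concern holds as a minor improvement. Section 4.3 suggests an agent that, taken up, dropped or used intermittently after B1, would move a primary end point with no change in phosphate handling. For one user the shift is 10–30% of FePI under the assumed creatinine rise. For a 40-person margin it is 0.2–0.7% with one extra user and 0.5–1.3% with two, and the test size stays within 5.0–6.5% on the table's visit days. Plasma phosphate and 24-hour urine phosphate are untouched by this route. The conclusion rests on the standard FePI formula, on general pharmacology for cimetidine, and on the assumed ranges above. The reason to act is that the change costs almost nothing; the trial's result is not in doubt.

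**What to change.** Delete cimetidine from the list in section 4.3 and keep famotidine, which the same sentence already names. Add one instruction asking participants not to take cimetidine from before B1 until F5. Optionally, add one question on acid-reducer use, by agent, at the existing visits.

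The cost is one drug name, one instruction and a minor wording amendment through the IRB. Sample size, visit schedule, assays and analysis do not change.

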4.4 Other Modalities or Procedures

N/A

4.5 Duration of Therapy

The intervention will last for 2 weeks.

4.6 Duration of Follow Up

Follow up will last for 2 weeks.

4.7 Removal of Participants from Protocol Therapy

Patients will be removed from therapy when any of the criteria listed in Section 5.6 apply.

4.8 Participant Replacement

N/A

5.0 STUDY PROCEDURES

There are 8 expected visits for the entire study. Study visits baseline 1 and follow-up 5 will take place at the NUCATS Clinical Research Center (CRU). The remaining visits will be completed at the Center for Translation Metabolism and Health (CTMH).

5.1 Recruitment

Subjects will be recruited using the NUCATS registry, Women's Health Research Institute registry, Illinois Men's Health Registry, ResearchMatch registry, newspaper and online advertisements, and an IRB-approved flyer. Potential participants from the registries will be sent an IRB-approved recruitment letter, recruitment e-mail, and contacted via telephone. Individuals solicited via Women's Health Registry and Men's

Health Registry will be sent recruitment letters specific to the registry. Newspaper and online advertisements will use IRB-approved advertisement.

5.2 Screening Procedures

Assessments performed exclusively to determine eligibility for this study will be done only after obtaining informed consent.

The screening procedures include:

5.2.1 *Informed Consent*

Consent form will be reviewed in full with each subject.

5.2.2 *Medical history and Physical Exam*

Complete medical and surgical history will be obtained from each subject, and a physical exam will be performed on each subject.

5.2.3 *Demographics*

Subject will be queried on age, gender, race, and ethnicity

5.2.4 *Review subject eligibility criteria*

Study personnel will review inclusion/exclusion criteria with every subject to determine eligibility.

5.2.5 *Review previous and concomitant medications, including multivitamins*

5.2.6 *Vital signs, height and weight*

Blood pressure, height, and weight will be obtained on each subject.

5.2.7 *Hematology*

CBC

5.2.8 *Plasma chemistries and Serum 25-Hydroxyvitamin D*

To include: albumin, alkaline phosphatase, ALT/SGPT, AST/SGOT, BUN, creatinine, electrolytes (sodium, potassium, chloride, bicarbonate), glucose, and total bilirubin; phosphorus; calcium; CK; and 25-hydroxyvitamin D

5.2.9 *Random urine*

To include: creatinine and albumin

5.2.10 *Supplies for 24-hr urine collection*

5.2.11 *Rapid Urine Pregnancy test (for females of child bearing potential)*

See section 3.1.6.1 for definition.

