3.1 Inclusion Criteria

3.1.1 Healthy volunteers

3.1.2 Age \geq 18 years, at the time of screening

3.1.3 Normal renal function at screening, as defined by

- eGFR > 60
- no albuminuria
- normal urinalysis
- normotensive, defined as blood pressure $< 140/85\text{mmHg}$
- no known history of CKD

3.1.4 Adequate organ and marrow function at screening as defined below:

- HCT	$\geq 30\%$
- platelets	$\geq 125,000/\text{mm}^3$

- total bilirubin	within normal institutional limits
- AST(SGOT)/ALT(SPGT)	$\leq 2.5 \times$ institutional upper limit
- 25-hydroxyvitamin D	$\geq 10\text{mg/dL}$

3.1.5 Women of child-bearing potential and men must agree to use adequate contraception (hormonal or barrier method of birth control; abstinence) prior to study entry, for the duration of study participation, and for 90 days following completion of therapy.

3.1.6 Ability to understand and the willingness to sign a written informed consent.

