5.4 Procedures During Treatment

During this period, participants will be randomized to the intervention arms (Baseline 2/ Follow up visit 0), have two 8-hour visits (Baseline visits 1 and Follow up visit 5) and will make visits to the CTMH every 3 days (Follow up visits 1 – 4).

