5.4.1 Baseline 2/Follow-up Visit 0 (F0)

- Return 24-hour urine collection to measure phosphorus, creatinine, calcium, and urea in the urine
- Random urine sample to measure phosphorus, creatinine, and calcium in the urine
- Plasma chemistries (NA, K, Cl, HCO3, BUN, Cr, glucose, phosphate, calcium)
- Blood draw for correlative studies (PTH, FGF23)
- Randomization to interventions
- Distribute study drug/placebo
- Distribute supplies for next 24-hr urine collection

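### The only pregnancy test is at screening, about two weeks before randomization and dispensing, and it is not repeated before the first dose

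*Combined protocol and SAP*

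**What the plan says.** Section 5.2.11 places a single "Rapid Urine Pregnancy test (for females of child bearing potential") among the screening procedures. In the Time and Events Table (5.5), the row "Pregnancy testing" has one mark, in the S1 column at Day -15.

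Section 5.4 states that "participants will be randomized to the intervention arms (Baseline 2/ Follow up visit 0"). The list for that visit (5.4.1) includes "Random urine sample to measure phosphorus, creatinine, and calcium in the urine" and "Distribute study drug/placebo", but no pregnancy test. The lists for Baseline 1 (5.3.1), F1 to F4 (5.4.2) and F5 (5.4.3) contain none either.

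Three other provisions bear on the point:

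- Section 3.3 requires the test before enrollment, with no maximum interval to first dose. Beside that rule it lists "Pregnancy or planning to become pregnant or currently breast-feeding".
- Section 3.1.5 requires agreement to contraception "prior to study entry, for the duration of study participation, and for 90 days following completion of therapy". It sets no minimum period of use before entry.
- Section 3.3.1 asks a woman who is, or thinks she may be, pregnant during the study to tell her physician at once.

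**The concern.** The protocol clearly means to keep pregnant women off study drug: it tests for pregnancy, lists it beside the test rule, and carries contraception to 90 days after therapy. Yet the last objective check comes about two weeks before the drug is handed out.

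A woman who conceived shortly before screening can test negative at S1 because it is too early. By Baseline 2/F0 the same test would probably be positive, but it is not done. Contraception agreed at screening cannot undo a conception that has already happened.

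What is at stake is an avoidable exposure in a healthy volunteer. The documents state no reproductive toxicity for either drug, so no size of harm is claimed.

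**Working it through.** The plan gives no figure of its own to reproduce. The check is a reading of the schedule, then day counts, then a rough expected yield.

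**1. Gap from test to dispensing (days from 5.5).** The table header lost its column alignment in the text available, so both readings are shown.

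- Visits and days matched in order, so that Baseline 2/F0 is Day -2: -2 - (-15) = 13 days.
- Day 0 column, where the randomization mark and the row "Distribute drug/placebo (X=21 day supply") appear to fall: 0 - (-15) = 15 days.

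**2. Which conceptions a repeat would add.** Assumption, not in the documents: a urine test misses the first 10 to 14 days after conception. The latest detectable conception day is then the test day minus the lag.

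| Repeat on | Lag | Latest conception seen at S1 | Latest seen at repeat | Days added | Before S1 | After S1 | Gap days still missed |
|---|---|---|---|---|---|---|---|
| Day -2 | 10 | -15 - 10 = -25 | -2 - 10 = -12 | 13 | 10 | 3 | 13 - 3 = 10 |
| Day -2 | 14 | -15 - 14 = -29 | -2 - 14 = -16 | 13 | 13 | 0 | 13 - 0 = 13 |
| Day 0 | 10 | -25 | 0 - 10 = -10 | 15 | 10 | 5 | 15 - 5 = 10 |
| Day 0 | 14 | -29 | 0 - 14 = -14 | 15 | 14 | 1 | 15 - 1 = 14 |

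Most of the added coverage lies before screening, which contraception agreed at screening cannot reach. Most conceptions after screening would still be missed.

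**3. Expected number found.** Further assumptions, not in the documents: 30 to 50 of the 80 participants are women of child-bearing potential, and 0.5% to 1% of them conceive per 30-day month.

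Expected number = women × (days added / 30) × monthly rate

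- Low end, Day -2: 30 × 13/30 × 0.005 = 0.065
- High end, Day -2: 50 × 13/30 × 0.01 = 0.217
- High end, Day 0: 50 × 15/30 × 0.01 = 0.25

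Split on the Day -2 reading:

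- Conceived before screening: 30 × 10/30 × 0.005 = 0.05 to 50 × 13/30 × 0.01 = 0.217.
- Conceived after screening: 0 to 50 × 3/30 × 0.01 = 0.05. On the Day 0 reading the upper end is 50 × 5/30 × 0.01 = 0.083.

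The rate before screening is the least certain input, since contraception may not yet have been in use. At 2% per month the upper totals are 50 × 13/30 × 0.02 = 0.433 (Day -2) and 50 × 15/30 × 0.02 = 0.50 (Day 0).

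**The case against.** The strongest reply is that nothing is broken. The S1 test satisfies section 3.3, and the protocol judges its other laboratory eligibility criteria at screening too; CBC, liver tests and CK are not repeated at Baseline 2/F0. Contraception is required, women are told to report a suspected pregnancy, and treatment lasts only two weeks. A repeat would still miss most conceptions after screening. The yield figures rest on a detection lag, a number of women and a conception rate that the documents do not give.

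Much of this stands. It is a design choice, not a violation; the probability is low; the coverage is partial; and only the 13 to 15 day gap can be verified from the documents. The counts show order of magnitude and no more.

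Two parts do not answer the point. Self-report depends on the woman suspecting a pregnancy, which is least likely when it is earliest, and it is not a test. The contraception rule has no minimum lead-in, so it leaves open the days just before screening, where a repeat adds most.

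**Conclusion.** The concern holds, as a minor safety point. The schedule has one pregnancy test, 13 to 15 days before dispensing, and the conclusion is the same on either reading of the table. Under the stated assumptions a repeat would find roughly 0.07 to 0.25 pregnancies over the whole trial, and up to 0.50 at the highest rate considered, so well under one case is expected. Confidence is high that no repeat is scheduled; the yield is only as good as its assumed inputs. The case for acting is that the participants are healthy volunteers, the safeguard serves the protocol's own intent, and it costs very little.

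**What to change.** In 5.4.1 and in the Baseline 2/F0 column of 5.5, add a rapid urine pregnancy test for women of child-bearing potential, run on the random urine already collected at that visit. Place it ahead of the randomization step and require a negative result before randomization and dispensing.

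The order matters. A woman found pregnant after randomization would remain a randomized but undosed member of a group of 20 (10.1). Section 4.8 on replacement says only that it does not apply, so the plan describes no way to replace her.

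The same edit can correct 5.2.11, which points to a section 3.1.6.1 that is not in the current text; the definition of child-bearing potential is in 3.3.1.

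The cost is one dipstick and a short wait per woman concerned, about 30 to 50 dipsticks on the assumed numbers, with no new visit or sample.
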